## 7.5 Blinding

To maintain objectivity,

- Pathologists will be blind to the reference diagnosis
- There will be a minimum six-week washout between reviews of the same sample using LM and DP
- The sequence of which modality (LM or DP) is used first will be randomised

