This study is designed around teams of four pathologists, blind to the original diagnoses, all examining the same series of samples, using both LM and DP. The modality each pathologist views/reports on first will be randomised for each batch of samples, and there will be a minimum of a six-week washout period between LM and DP viewings. Reports will then be scrutinised by a trained Research Fellow independent of the reporting pathologists. Differences detected will be classified by an independent pathologist into clinically important (would alter the clinical management) or clinically unimportant (would not alter the clinical management). The original diagnosis will serve as the reference diagnosis. The ground truth (GT) for each sample is decided on conclusion of the readings, by consensus of the study pathologists, taking into account the reference diagnosis. This allows comparison of each pathologist's performance on LM and DP against the GT. The study will examine 2000 histopathology samples including 600 samples each of breast, gastrointestinal (including 200 cancer screening samples) and skin, and 200 renal samples taken for native or transplant related renal disease. The renal biopsies will include immunofluorescence for detection of immunoglobulin deposits. The population of samples enrolled will be a combination of sequentially selected samples and those from study centres' archives. With the exception of renal, samples will also be enriched with at least 10% moderately difficult and at least 10% difficult samples.

A Health Economic evaluation will involve estimating the core costs and benefits associated with DP, compared with LM. This will involve estimating the impact of switching to DP on throughput, and translating this into the impact on the time to establishing a treatment plan. It will further involve assessing samples of discrepancy to investigate the impact on treatment decisions, and the incremental costs and benefits resulting from this impact. This will be for all discrepancies if feasible, or a purposive sample (selected based on material impact on health and cost outcomes).

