## 7.2.1 Samples from Belfast, Nottingham and Lincoln (breast, GI and skin)

The pathologist at site will identify each sample for the study following its routine diagnosis and pass it to their technicians for processing and shipping to Coventry coordinating centre. Upon receipt of the sample from the pathologist, the technician will need to:

- Enrol each sample on the Warwick Clinical Trials Unit (WCTU) database system. Sample details including non-identifiable patient details, sample difficulty level, number of parts/blocks/slides, reference diagnosis etc will need to be provided as part of the enrolment process.
- Pseudonymise the slides and associated histopathology report(s) by redacting all patient identifiable information leaving only the histology number visible. This will enable the samples to be returned to their original site once the study has been completed. The pseudonymised histopathology report(s) will need to be provided during the enrolment process, either as a file upload or as free text.
- Log the sample(s) as being sent to Coventry coordinating centre, as per local SOP and on the WCTU database system. The database will alert the coordinating centre about this forthcoming shipment.
- Send the sample(s) to Coventry coordinating centre

When the samples are received by Coventry coordinating centre, each sample will be checked for quality control (for example that slides are in good condition) prior to being scanned onto the IMS. If all criteria are met, the sample will be allocated a unique 'study number' generated by the database system. The study number certifies the sample as fully anonymised. This study number, along with other details, will be barcoded by trained coordinating staff using the current UHCW process, and the barcode will be placed on the slides. Following this, the slides will be immediately digitised.

If the sample selection criteria are not met, the case is declined. The sample is marked as ineligible on the WCTU database then returned to the originating site. Return of the sample is tracked on the WCTU database.

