## 7.2.2 Samples from Coventry (breast, GI and skin)

A similar process as above will be followed for samples identified from Coventry site, including the allocation of study numbers and barcode labelling, so that these samples are not identifiable to the research team at Coventry.

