## 7.2.3 Samples from Oxford (renal)

Renal samples will be enrolled from Oxford only. Pathologists identify the sample(s) for the study and pass to their technicians. Technicians then need to:

- Enrol each sample on the WCTU database system. Sample details including non-identifiable patient details, number of parts/blocks/slides, reference diagnosis etc will need to be provided as part of the enrolment process.
- Pseudonymise the histopathology report(s) by redacting all patient identifiable information leaving only the histology number visible. The pseudonymised histopathology report(s) will need to be provided during the enrolment process, either as a file upload or as free text.
- The WCTU database system will produce a unique anonymised study number for each enrolled sample.

- Label the sample slides with the study number. If applicable, immunofluorescence (IF) stained slides of the original image will be anonymised with the same study number and used for the study.
- Digitise the slides
- Log the sample(s) as being sent to Coventry coordinating centre, as per the existing local laboratory SOP and on the WCTU database system, using the unique study number in the record. The database will alert the coordinating centre about this forthcoming shipment.
- Send the sample(s) to Coventry coordinating centre

Quality control and eligibility checks of renal samples at Coventry coordinating centre will follow the same process as for breast, GI and skin.

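### Reader blinding to the original diagnosis is asserted but not secured: nothing keeps a reader off a case they signed out or nominated, and the plan does not say this is recorded

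*Protocol*

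**What the plan says.** Section 7.5 of the protocol lists three protections: "Pathologists will be blind to the reference diagnosis", a washout of at least six weeks between the two reads, and randomised modality order. Section 2 repeats the blinding ("This study is designed around teams of four pathologists, blind to the original diagnoses, all examining the same series of samples") and says what is being hidden: "The original diagnosis will serve as the reference diagnosis".

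The sampling rules are in section 7.2:
- **Belfast, Nottingham and Lincoln (7.2.1):** "The pathologist at site will identify each sample for the study following its routine diagnosis and pass it to their technicians".
- **Coventry (7.2.2):** "A similar process as above will be followed for samples identified from Coventry site".
- **Oxford (7.2.3):** "Renal samples will be enrolled from Oxford only. Pathologists identify the sample(s) for the study and pass to their technicians".

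At the first three sites slides and reports are pseudonymised by "redacting all patient identifiable information leaving only the histology number visible", so that samples can go back to their site. Coventry then adds a study number and barcode. At Oxford the visible-number wording covers the report only, and the slides are labelled with the study number.

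Section 7.4 places the readers at these same sites, plus one at Birmingham, and has all four readers of a specialty report the whole series on both platforms. Section 7.6 starts the washout clock when a reader finishes the first study read. Section 18.5 requires the discordance adjudicator to be uninvolved in reporting the samples. No matching rule is stated for readers.

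**The concern.** A reader who signed out a case, or picked it for the study, has already seen the answer the blinding is meant to hide. The protocol does not bar that reader from the case, does not say that selectors are non-readers, and sets no interval between sign-out or selection and the first study read. The washout exists because seeing a case once can influence the next read. The same reasoning applies to the earlier viewing, which the washout does not cover.

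The primary outcome is agreement between a pathologist's own DP and LM diagnoses. Recall of the original diagnosis acts on both reads in the same direction, so randomising modality order does not balance it out; it makes the platforms look more alike. The secondary comparisons with the ground truth are exposed too, because the ground truth is settled by the study pathologists and draws on the reference diagnosis. In breast, GI and skin, the deliberately chosen difficult cases are plausibly the most memorable, and they are also where agreement has most room to rise.

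**Working it through.** **1. Do the safeguards cover own-case reads?**
- *Washout (7.5, 7.6):* runs from first to second study read only.
- *Study number and barcode (7.2.1 to 7.2.3):* hide identity on the label, but not morphology. For breast, GI and skin slides, nothing says the barcode covers the histology number left visible earlier.
- *Independence rule (18.5):* applies to the adjudicator only.
- *Figure 3 legend:* gives no exclusion. The flow diagrams themselves are not available to check.

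**2. How many readers sit at a supplying site?** Source sites are from section 7.1, readers from the table in 7.4.

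| Specialty | Source sites (readers there) | Readers at a source site |
|---|---|---|
| GI | Coventry 1, Belfast 2, Nottingham 1 | 4 of 4 |
| Skin | Coventry 2, Belfast 1, Lincoln 1 | 4 of 4 |
| Breast | Belfast 1, Lincoln 1, Nottingham 2, Coventry 0 | 4 of 4 |
| Renal | Oxford 2 | 2 of 4 |

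Total: 14 of 16. The other two renal readers are at Coventry and Birmingham.

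**3. Upper bound on own-case reads.** Home-site pairs = sum over sites of (samples from site × readers at site). The protocol gives no split by site, so equal shares are an assumption.
- GI: 200 × (1+2+1) = 800 of 2,400 (33%); any split, 25% to 50%
- Skin: 200 × (2+1+1) = 800 of 2,400 (33%); any split, 25% to 50%
- Breast: 150 × (1+1+2+0) = 600 of 2,400 (25%); any split, 0% to 50%
- Renal: 200 × 2 = 400 of 800 (50%) at any split
- All: 2,600 of 8,000 (32.5%); any split, 1,600 to 4,000 (20% to 50%)

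**4. Possible size of the inflation (illustration only).** Suppose a share m of home-site reads are own cases that are recalled and so always agree. Then observed concordance = p + f × m × (1 − p), where f is the home-site share. With f = 1/3 and m from 0.1 to 0.5:
- p = 90% (the planned overall value) becomes 90.3% to 91.7%.
- p = 55% (the planned value for difficult samples) becomes 56.5% to 62.5%.

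The documents give no value for m.

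**5. Cost in precision of dropping every home-site read.** Margin = 1.96 × √(p(1−p)/n_eff), with n_eff = (Σm)² / Σ[m(1+(m−1)ICC)] summed over samples, where m here is the number of readers kept per sample and p = 90%.
- *Plan's own figure, section 12.1:* 2,400/3.4 = 705.9, giving 2.21% (stated 2.2%).
- *Breast, ICC 0.8:* readers kept are 3, 3, 2, 4. n_eff = 1,800² / [150 × (7.8+7.8+3.6+13.6)] = 3,240,000/4,920 = 658.5, giving 2.29%.
- *GI, ICC 0.8:* readers kept are 3, 2, 3. n_eff = 1,600² / [200 × (7.8+3.6+7.8)] = 2,560,000/3,840 = 666.7, giving 2.28%. Skin has the same pattern and result.
- *Renal:* the stated 3.1% is reproduced with ICC 0.4: 800/2.2 = 363.6, giving 3.08%. With two readers: 400/1.4 = 285.7, giving 3.48%.

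**The case against.** The strongest reply is that the protocol does require blinding and simply does not spell out the mechanism. Sections 7.2.1 and 7.2.3 refer to pathologists at site without saying that they are study readers or the original reporters. This stands: overlap is permitted, not stated. A reader might infer that the readers choose their own cases, or that the sections contradict each other outright. The text supports neither.

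Other parts of the reply also stand:
- Relabelling is a real safeguard. The visible histology number cannot be argued against renal slides, which carry the study number.
- Shipping, scanning and batching delay the first read, and some samples come from archives. No minimum interval is set, however, and nominating an archive case shows it to the nominator again.
- Renal samples are sequential and unenriched, so the argument about memorable, hand-picked cases does not apply there. Prior sign-out still can.
- Supplying sites are not always reading sites: Coventry supplies breast samples and has no breast reader.
- About 80% of breast, GI and skin samples are planned as routine with 98.8% concordance, leaving at most 1.2 points of inflation in that stratum. The exposure is mainly in the moderate and difficult strata.

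It can also be said that sensitivity analyses belong in a statistical analysis plan, which is not at hand. Their absence is not the complaint. Who may select and read a case is protocol content, and unless the original reporter and selector are recorded, no later analysis can separate the affected reads. The enrolment list in 7.2.1 is open-ended, so such a field might exist, but none is stated.

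**Conclusion.** The point holds as a gap between a stated protection and the procedures meant to deliver it. As written, a reader may report a case they signed out or nominated, and the likely direction of any resulting bias is towards higher DP-LM agreement and higher agreement with the ground truth.

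The number of own-case reads is unknown. It is tempting to read 32.5% as the contaminated share. It is not: it counts every home-site read, at an assumed equal site split, and so only bounds the own-case share (20% to 50% over all splits, with renal fixed at 50%). Under the illustrative recall assumptions, the effect on overall concordance in GI or skin is about 0.3 to 1.7 points, inside the planned 2.2% margin. In difficult samples it is about 1.5 to 7.5 points.

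Nor do the documents support removing home-site or own-case reads from the primary analysis, because section 7.4 builds the study on all four readers reporting the same series. For the renal cost, the right baseline is the protocol's 3.1%. Working from the difficult-sample values (55%, ICC 0.4) would give 5.1%, which is not the plan's figure.

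**What to change.** - **Record it.** Add an enrolment item stating whether any study reader originally reported or selected the case, and which one. This cannot be left until analysis.
- **Separate the roles where possible.** Have samples nominated by non-reading staff at sites that already have them, and state in section 7.5 whether selectors and original reporters may be readers.
- **Mask the number.** State that the histology number on breast, GI and skin slides is covered while slides circulate, with return to site tracked through the study number in the database, which already tracks the return of declined samples.
- **Analyse it.** Keep the four-reader primary analysis. Pre-specify one sensitivity analysis without own-case reads and a second without all home-site reads.

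The cost is one enrolment field, some masking effort, and slightly wider margins in the sensitivity analysis. At worst, dropping all home-site reads, these go from 2.21% to about 2.29% for breast and 2.28% for GI and skin (equal site split), and from 3.1% to about 3.5% for renal (90% concordance, ICC 0.4). One limit remains: in renal the second analysis rests on two readers outside Oxford, so a change there could reflect different readers as well as recall.

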## 7.6 Distribution and tracking of samples following enrolment, batching and randomisation

Following batching and randomisation, the two pathologists in the 'DP first' group will be assigned the digital images. These pathologists will view the samples on the Philips Image Management System (IMS) and report their findings using WCTU database system's electronic Case Report Form (eCRF). Once one of these pathologists has completed the reporting of the entire batch, the system will prompt the technicians at Coventry coordinating centre to package up the glass slides and dispatch to the first pathologist in the 'LM first' group.

As and when a site receives a batch of glass slides, the technician (or other trained staff member) should record the received date on the WCTU database system and check the condition of the slides, then pass them on to the pathologist for viewing and reporting.

Once the first pathologist in the 'LM first' group has completed reporting, the system will prompt the pathologist to pass the slides back to the technician(s). The technician(s) will then send the glass slides to the site at which the second pathologist in the 'LM first' group is based.

For each of the pathologists, a 6 week washout period begins from the date on which their first read is completed.

For the second reads, the glass slides will be made available to the pathologists in the 'DP first' group (one followed by the other, in a fixed order, and only when each pathologist's 6 week washout period has ended). The glass slides will then be returned to Coventry coordinating centre.

When 6 weeks have passed since the completion of the 'LM first' pathologists' first reads, the WCTU database system will prompt the technicians at Coventry coordinating centre to assign the digital images to the 'LM first' pathologists.

## 7.7 Sample pathway flow diagrams

[figure not shown]

Figure 1: Study flow diagram - Breast, GI & skin samples

Page **17** of **38** 

[figure not shown]
[figure not shown]
[figure not shown]

Figure 2: Study flow diagram – Renal samples

Page **18** of **38** 

#### Figure 3: Sample reporting

**Legend:** Belfast, Coventry, Lincoln and Nottingham enrol reported samples of breast, gastrointestinal and skin. Renal biopsy samples are enrolled by Oxford only. These samples are divided into batches and randomised to which pathologists review on DP first and which on LM first (Read 1). Curved arrows indicate circulation of batched samples between the LM reviewing pathologists. After 6 weeks, pathologists swap to the alternative platform in Read 2. For each sample where there is considered to be a clinically important difference between reports, participating pathologists meet after read 2 to agree the ground truth diagnosis.

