While most previous studies show good LM/DP agreement, (6) (7, 8) (9) some (10) raise concerns over the suitability of DP for diagnosis. Particular concern has been raised about the use of DP for examining samples taken as part of the NHS cancer screening programmes for breast, bowel and cervical cancers.

Our team includes UK leaders in pathology at six NHS teaching hospitals and a large pathology network. We have world leading experience in DP having pioneered its use in routine practice, as well as vast experience of pathology practice and research. The pathologists taking part are a diverse group including highly experienced, relatively junior, early adopters of DP and - a majority - new to DP. The study plan is based on eight viewings of each sample by four pathologists with LM and also with DP, culminating in a consensus ground truth (GT), enabling measurement of agreement within and between readers. Samples enrolled will reflect routine practice. The samples will include cancer screening biopsies and will be enriched for areas of difficulty such as dysplasia (7, 10, 11). State-of-the-art DP equipment designed for diagnosis and holding either CE or FDA approval will be used in this study.

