## **11. END OF STUDY**

The completion of the ground truth and analysis of all reports by consensus diagnosis will be considered as end of study.

The study will be stopped prematurely if funding for the study ceases.

The Health Research Authority will be notified in writing within 90 days when the study has been concluded or within 15 days if terminated early.

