## **12.2** Statistical analysis plan

#### Primary analysis

There will be three categories for the level of agreement: complete agreement, clinically unimportant difference and clinically important difference. For each sample, three sets of agreements will be reported:

- whether each pathologist's DP and LM diagnoses concur
- whether each of the four DP diagnoses concur with the GT
- whether each of the four LM diagnoses concur with the GT

Two measures will be used to quantify concordance: percentage concordance and ICC. Logistic regression models will be used to estimate the probability that diagnoses are concordant and will include a random effects term to account for multiple results per sample.

For cancer resections, as well as diagnosis, comparisons will also be made across all RCPath dataset items.

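### Section 2 and the Figure 3 legend give different rules for the ground truth, and the Figure 3 rule leaves two groups of samples without a sound one

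*Protocol*

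**What the plan says.** The protocol describes the GT in several places.

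- Section 2: "The ground truth (GT) for each sample is decided on conclusion of the readings, by consensus of the study pathologists", and this is done "taking into account the reference diagnosis". The original diagnosis is the reference diagnosis.
- Section 3: the eight viewings are described as "culminating in a consensus ground truth (GT), enabling measurement of agreement within and between readers".
- Section 7.7, Figure 3 legend: "For each sample where there is considered to be a clinically important difference between reports, participating pathologists meet after read 2" to settle the GT. The reference diagnosis is not mentioned.
- Section 11: "The completion of the ground truth and analysis of all reports by consensus diagnosis will be considered as end of study".
- Section 12.2, Primary analysis: the scale is "complete agreement, clinically unimportant difference and clinically important difference". It continues: "For each sample, three sets of agreements will be reported". One set is "whether each of the four DP diagnoses concur with the GT", another is the same for the four LM diagnoses, and the remaining set is each pathologist's DP against LM.
- Section 18.5: the steering committee monitors clinically important and unimportant differences between GT and reference diagnosis.

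Section 6 defines the primary outcome as within-pathologist DP-LM agreement. Agreement with the GT is listed there as secondary.

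**The concern.** The GT is the reference standard for two of the three sets of agreement. Sections 2, 3, 11 and 12.2 all need one for every sample. The Figure 3 legend describes a meeting for only some samples, triggered by disagreement among reports, and leaves out the reference diagnosis that section 2 brings in. The two descriptions differ on which samples go to consensus and on what information enters it. Teams following one or the other would do different work.

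Two things are at stake. First, a three-level score needs a GT specific enough to separate complete agreement from an unimportant difference, and under Figure 3 no rule supplies one where reports differ only in minor ways. Second, a trigger that looks only at disagreement between readers cannot pick up a departure from the reference that all readers share. If such samples are then scored against the shared reading, DP-GT and LM-GT agreement both rise.

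**Working it through.** **Comparing the rules by type of sample.** I read "reports" in the legend as the study reports, which is its natural meaning although the legend does not define it. I worked from the legend because the flow diagrams themselves were not visible in the text available to me.

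| Pattern in a sample | Section 2 | Figure 3, literal | Usable GT for section 12.2? |
|---|---|---|---|
| Clinically important difference between reports | Consensus, reference considered | Meeting | Yes, but the role of the reference differs |
| All reports agree, and agree with the reference | Consensus | No meeting | Yes: the common diagnosis is an obvious GT, though not stated |
| (a) Only clinically unimportant differences | Consensus | No meeting | No: nothing says which diagnosis is the GT |
| (b) All reports agree but differ importantly from the reference | Consensus, reference considered | No meeting | No stated rule and no consensus review |

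**How many samples would reach a meeting.** The protocol gives no figure, so there is none to reproduce. As a proxy I took the chance of at least one discordance in a sample, using these inputs:

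- Section 12.1: concordance c = 0.988 routine, 0.75 moderate, 0.55 difficult; ICC ρ = 0.9, 0.7, 0.4; mix 80/10/10.
- Section 7.1: 1800 breast, GI and skin samples, and 200 renal samples, all regarded as difficult.
- Section 7.4: four pathologists, each reading on both modalities, so four DP-LM pairs and eight reports.

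Four dependence assumptions were used:

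1. Fully correlated pairs: P = 1 − c.
2. Beta-binomial with the protocol's ICCs: a = c(1−ρ)/ρ, b = (1−c)(1−ρ)/ρ, and P = 1 − the product over i = 0 to 3 of (a+i)/(a+b+i). For difficult samples a = 0.55 × 0.6/0.4 = 0.825 and a+b = 1.5, so P = 1 − 0.55 × 0.73 × 0.807 × 0.85 = 0.725.
3. Independent pairs: P = 1 − c⁴.
4. Eight independent reports with two possible diagnoses: solve 1 − c = 2q(1−q), then P = 1 − [(1−q)⁸ + q⁸].

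| Assumption | Routine | Moderate | Difficult (and renal) | Breast, GI, skin | All 2000 |
|---|---|---|---|---|---|
| 1 | 1.2% | 25.0% | 45.0% | 8.0% | 233 (11.7%) |
| 2 | 1.4% | 35.8% | 72.5% | 12.0% | 360 (18.0%) |
| 3 | 4.7% | 68.4% | 90.8% | 19.7% | 536 (26.8%) |
| 4 | 4.7% | 71.8% | 96.5% | 20.6% | 564 (28.2%) |

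For example, under assumption 2: 1800 × 0.1196 + 200 × 0.7245 = 215 + 145 = 360.

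So between 2000 − 564 = 1436 and 2000 − 233 = 1767 samples would have no meeting. That is the number on which the two rules differ procedurally. It does not measure groups (a) and (b), because it includes every sample in which all reports and the reference agree.

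**The case against.** The strongest reply is that the passages can largely be read together. The legend says when pathologists meet, and section 2 says the GT is reached by consensus. Where all reads coincide there is consensus without a meeting. This stands for fully agreed samples. A reader might infer from the table that Figure 3 leaves most samples without a consensus GT, but the documents do not support that. The fault there is only that the protocol does not say so.

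A reader might also infer that in group (b) the shared reading becomes the GT by default and all eight reads count as correct. No passage states such a default, and the legend does not withdraw section 2's use of the reference. The overstatement is therefore a risk, not a stated rule.

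Nor does it follow that section 18.5's check of GT against reference never operates for these samples. That check does not depend on a meeting. It does need a GT to compare, which Figure 3 does not supply for group (b), and it describes committee action, not revision of the GT. An error shared by all eight reads and the reference would probably survive either rule.

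Finally, scoring detail is often left to an analysis plan. Here, however, the protocol itself describes the operational rule twice, differently. None of these replies closes group (a).

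**Conclusion.** The two descriptions of the GT need to be reconciled. Figure 3 taken literally gives no GT rule for samples with only unimportant differences, and no consensus review where all study reports agree but depart importantly from the reference.

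The affected results are the DP-GT and LM-GT agreements. Section 12.2 lists them under Primary analysis, so a reader might think the primary outcome is at risk. It is not, because within-pathologist DP-LM agreement does not use the GT. This is a correction that should be made, not one that undermines the study.

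Groups (a) and (b) cannot be sized from the protocol, and no estimate of the overstatement is possible. The 12% to 28% reaching a meeting is a guide, not a bound. It lets within-reader discordance stand in for clinically important differences across all eight reports, and section 12.1 gives neither a between-pathologist rate nor a split by clinical importance. For renal, 72% to 97% would reach a meeting under three of the four assumptions and 45% under the fourth, so the gap there is probably smaller.

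**What to change.** State one rule in section 12.2 and bring section 2 and the Figure 3 legend into line with it:

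- A GT is recorded for every sample.
- Consensus is triggered by a clinically important difference between any two study reports, or between any study report and the reference diagnosis.
- Where all reports agree with each other and with the reference, that diagnosis is the GT.
- Where there are only clinically unimportant differences, the diagnosis that serves as the GT is fixed in advance, before any GT is assigned.

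Making the reference the GT in every sample without a meeting would be simpler, but it would replace section 2's consensus with a single original report. I do not suggest it.

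The cost is wording, one comparison of the reports with the reference diagnosis already recorded at enrolment, and what should be a small number of extra consensus samples.
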